SQ3370 consists of 2 components: SQP33, a Dox prodrug, and SQL70, a biopolymer. SQL70 biopolymer is injected on Day 1 of each 21-day cycle into a lesion or lesions followed by 5 consecutive daily infusions of SQP33 prodrug (Day 1-5). No more than 2 lesions may be injected during the treatment cycle with the exception of a “regional cluster of lesions”.

Patients may continue to receive treatment for up to 12 cycles. Treatment for more than 12 cycles requires approval by the Medical Monitor. All lesions should continue to be injected until either:

- they are no longer injectable (as determined by the investigator): this includes lesions that are resolved, no longer clearly seen on scan, no longer palpable, cannot continue to be safely injected, or are either suspected or confirmed on biopsy to no longer contain viable tumor. At this point the area of the tumor bed, if possible, should be treated for a minimum of at least two additional cycles.
- they have progressed per RECIST v1.1
- or other treatment discontinuation criteria are met (see section [3.1.5 End of Treatment](#))
- See [APPENDIX G – Schedule of Assessments – Phase 1 Dose Escalation](#) for details.

Phase 2: Expansion Groups

- Group 1: Extremity STS
 - Subjects with soft tissue sarcomas of the extremity AJCC Stage III OR IV (> 5 cm injectable tumors) locally advanced and or metastatic, not amendable to primary surgical intervention, according to the consensus of a multidisciplinary treatment team, determined prior to screening.
 - Group 1 will be conducted in 2 phases with a possible expansion phase. The group will open with a) the initial phase safety run-in of 6 patients to establish the safety and initial feasibility of a 12-week delay in definitive surgical resection in patients with high-risk STS of the extremity treated with SQ3370, and b) 31 additional patients initial adaptive design phase.

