1.1.1. Soft-tissue Sarcoma

Soft tissue sarcomas are a rare group of heterogeneous malignancies with >50 histologic subtypes that have varying biological behavior and responsiveness to therapy. Surgery with radiotherapy is the most common treatment for localized disease when resection is possible, with associated 5-year overall survival of 55% ([Seddon 2017](#)). Survival outcomes for locally advanced or metastatic STS poor, with a median overall survival of 12.8-14.3 months after diagnosis ([Verschoor 2020, Judson 2014](#)).

With modern limb salvage techniques, amputation for extremity soft tissue sarcomas is now rare. A study that reviewed patients where amputation was used for local control compared to limb conservation showed the rates of systemic relapse and disease-specific survival were poorer in the amputation patients, with a 3 year overall survival of only 50.3% following curative amputation, while those patients undergoing limb salvage had a greater than 75% overall survival. Of the 59 patients with localized disease at the time of amputation, 29 developed metastatic disease (49.2%), with a median time to first metastasis of 10 months ([Smith 2017](#)). Amputation patients are a high risk group of soft tissue sarcoma patients where improved treatments are needed.

Doxorubicin has been the mainstay of first-line treatment for locally advanced, unresectable, or metastatic STS for decades, achieving objective response rates of 0–20% ([Seddon 2017, Chawla 2015, Tap 2017](#)), median progression-free survival (PFS) of 23.3 weeks ([Seddon 2017](#)), and a median OS of 12.8 months ([Verschoor 2020](#)). More recent trials report slightly better median OS for doxorubicin monotherapy with 16.9 months ([Ryan 2016](#)), 17.6 months ([Seddon 2017](#)), and 19.0 months ([Tap 2017](#)) respectively ([Ryan 2016](#)). A randomized controlled Phase 3 trial ([Judson 2014](#)) comparing combination Dox and ifosfamide versus Dox alone showed a significant increase in PFS in the combination treatment group, but with no increase in OS. Further, in a recent retrospective database analysis of 2045 patients from 12 EORTC sarcoma trials (inclusion period 1980–2012) after completing 6-cycles of first line Dox monotherapy or

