3.2.7. Safety Review Committee (Dose Escalation and Phase 2a)

The SRC will include the study team led by the medial monitor, and the active Investigator(s). The SRC will review all available safety data at the completion of Cycle 1 for each cohort to evaluate possible DLTs, recommend whether more patients should be enrolled at a given dose level / cohort, and whether to dose escalate or to stop enrollment based on the definition of DLTs in addition to its members' best clinical judgement and will provide recommendations to the sponsor.

With agreement from the sponsor, the dose escalation scheme may be modified (e.g., smaller increases or decreases in dose may be permitted, infusion timing, duration, or schedule may be modified) based on available PK and pharmacodynamic data, and/or the timing and severity of AEs observed. Changes that can only be made with a protocol amendment will include:

- Dose level escalations that are increased by larger increments than the scheme in the protocol
- Administration of more than 5 SQP33 infusions per cycle
- Administration of more than 20 mL of SQL70 biopolymer per cycle

Phase 2a Responsibility

In Phase 2a, the SRC will utilize the same criteria to evaluate the safety and tolerability of all available safety data at the completion of timing for each group to determine the initial safety and monitor the groups throughout the study overall safety and tolerability.

Table 4: Phase 2a Safety Evaluation Timing

Group	Run-in Evaluation N= (timing)	Simon 2 Stage 1 evaluation	Final Assessment
1: Extremity STS	N=6 (after cycle 1)	N=15	N=46
2: STS unresectable	N=12 (6 per arm; after cycle 2)	N.A.	N=22
3a: Head and Neck	N.A.	N=13	N=26

N.A.= Not Applicable

A run-in is not planned for the Head & Neck group (Group 3a) since they will be receiving the RP2D and schedule of SQ3370 without modifications (see [Table 4](#)).

Group 1 will receive SLQ70 in a volume of 20 mL with the RP2D of SQP33 and therefore the safety lead-in to this group is warranted. The SRC may, after the planned initial review of any group, within its purview recommend additional monitoring to the sponsor.

[figure not shown]

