3.5. RATIONALE FOR STUDY DESIGN AND DOSE

3.5.1. Rationale for Study Design and Objectives

This is a first-in-human, Phase 1/2a study in patients with advanced solid tumors. Phase 1 will explore escalating doses of SQP33 protodrug and SQL70 biopolymer (see section [3.1 Overview](#)) to identify the MTD and/or RP2D of SQP33 protodrug with 10 mL and/or 20 mL of SQL70 biopolymer. The accelerated titration and 3+3 (Rolling 6) design are being used to evaluate safety and tolerability of SQ3370. During the study, PK will be evaluated to determine the amount of systemic and localized active Dox following SQ3370 treatment.

Phase 2a will utilize the RP2D determined in Phase 1. Three Expansion Groups will further explore the safety and preliminary efficacy of SQ3370 in different patient populations.

Group 1: Advanced High-risk Soft Tissue Sarcoma of the Extremity

Resectable is defined for the study as a primary surgical intervention that is thought to produce a surgical cure and maintain a good functional outcome of the affected extremity. The study will enroll patients with unresectable soft tissue sarcomas of the extremity AJCC III OR select IV (>5 cm injectable tumors) locally advanced and or metastatic that meet the preceding injectable tumor criteria not amendable to primary surgical intervention according to the consensus of multidisciplinary treatment team, determined prior to screening.

The study will be conducted in 2 phases with a Simon 2 stage design in the 2nd phase. The group will open with the initial phase safety run-in of patients to establish the safety and initial feasibility of a 12-week delay in definitive surgical resection in patients with high-risk STS of the extremity treated with SQ3370, after review by the safety steering committee the Simon 2 stage design will initiate subjects enrolled in the lead-in will contribute to this phase of the study.

Patients will enroll at the RP2D of SQ3370 as anticipated that the size of tumors given the stage (≥ 2) will receive a fixed dose of SQL70 (20 mL). All patients are planned to receive 2 cycles of SQ3370 and undergo a disease reevaluation per RECIST 1.1. All patients without evidence of disease progression after 2 cycles, will then undergo an additional 2 cycles of treatment and have a presurgical disease re-evaluation and proceed to definitive surgical procedure(s) of the extremity tumor.

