Only patients who have had objective evidence of response or whom in the opinion of the multidisciplinary treatment team determined to have achieved a clinical benefit may defer surgery at this point, the study will allow up to 4 additional cycles pre-operatively, at which point all patients should undergo exploratory surgery and or extremity tumor resection.

If a patient had a response, they may receive up to 4 additional cycles post operatively but not to exceed 12 cycles within the study. Surgical markers will be used to indicate the tumor bed for injection with SQL3370 or if suitable for the metastatic patients, a metastatic lesion may be injected.

Any patient at any point who has been determined to have progressive disease has reached the end of treatment and will proceed to a definitive surgical treatment, note pre-operative radiation is allowed on study for patients with progressive disease preoperatively. It is encouraged to keep subjects on study and to evaluate surgical specimens as per planned biomarker and pathological assessments.

Patients who undergo surgical resection and have had good response as defined by necrosis on histopathological resection may continue for additional treatment post-operatively. If post op radiation is administered the subjects come off treatment (see [3.1.5 End of Treatment](#) for details) and will remain on study in Long Term Follow-up.

Safety Monitoring

The Study will use a safety-run-in to evaluate the PK and tolerability when at least 6 subjects have been enrolled and completed at least the planned Cycle 1. All available safety tolerability data will be presented and discussed at the SRC.

If after the evaluation by the SRC the study proceeds after evaluation of the initial subjects a second evaluation as defined in the statistical section. An evaluation of the totality of the data available to complete the planned 4 cycles and to review efficacy and histopathological response data and will provide the sponsor a recommendation as to proceed with expansion or to halt enrollment of the group.

Group 2: Comparison of the RP2D of SQP33 Administered Over 3 vs 5 Days

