8.3. DETERMINATION OF SAMPLE SIZE

Phase 1 Dose Escalation: Sample size for the dose escalation portion of the study is not predefined; total enrollment will depend on the DLTs observed and number of escalation cohorts.

Phase 2a Expansion Groups:

Groups 1 (Extremity STS) and 3a (Head and Neck)

Sample sizes are guided by Simon 2-stage (optimal) designs based on historical objective responses per indication. Because of the different participant populations (sarcoma and H&N cancers), different criteria are applied to determine the number of participants for each stage and the strength of the efficacy signal that would recommend proceeding to the next stage. Details are described in subsequent sections and in [Table 9](#).

Table 9: Simon 2-Stage Design

Cohort	Power	Historical ORR/Target ORR	Stage 1 responders/ Stage 1 n	Stage 2 responders/ Stage 2 n	Consider Futility	Go to Stage 2	Consider Futility	Consider Efficacy	Expected Sample Size
H&N	85%	20%/45%	≤3/13	≥4/13		≤8/26		≥9/26	16.28
Extremity Sarcoma	70%	20%/35%	≤3/15	≥4/15		≤13/46		≥14/46	25.91

For sample size calculation and for simplicity of description, recommendations for stopping or progressing to the next stage are based on the number of objective responses observed. However, since best overall response (BOR) does not necessarily capture the full extent of clinical benefit and since response can be delayed or of short duration, Shasqi will also review other aspects of clinical benefit that may better predict PFS or OS benefit, such as DOR, before making a final determination.

Enrollment will be continued after reaching the indicated number of participants at Stage 1 while the initial efficacy evaluation is ongoing. This will allow additional participants to enroll to account for unexpected trial impact, such as response non-evaluable participants due to early dropout, design parameter change (e.g., historical response rate update), etc. Although the sample size calculations are based on efficacy considerations, safety will also be continuously assessed and will be considered in the decision to continue or terminate a study treatment population.

Under the optimal Simon 2-stage design criterion:

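### The Group 1 run-in is meant to establish the safety and initial feasibility of a 12-week delay of surgery, but its only scheduled review comes after Cycle 1 and covers PK and tolerability

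*Protocol*

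**What the plan says.** **Aim.** The Synopsis (Treatment Groups and Regimens, Group 1) gives the run-in as "the initial phase safety run-in of 6 patients to establish the safety and initial feasibility of a 12-week delay in definitive surgical resection". Protocol 3.5.1 and the Phase 2a SAP (2.3) state the same purpose.

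**Run-in review.** The Group 1 run-in entry in Table 4 (Protocol 3.2.7) is "N=6 (after cycle 1"), and SAP 7.1 repeats it. Protocol 3.5.1 says the run-in is "to evaluate the PK and tolerability when at least 6 subjects have been enrolled and completed at least the planned Cycle 1". Section 3.2.7 justifies the lead-in by the 20 mL SQL70 volume given with the RP2D and does not mention surgical delay. SAP 7.1 calls this look safety/tolerability.

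**What follows it.** In 3.5.1, "after review by the safety steering committee the Simon 2 stage design will initiate", with the lead-in patients counted in it. A second evaluation follows: "An evaluation of the totality of the data available to complete the planned 4 cycles and to review efficacy and histopathological response data", ending in a recommendation to expand or halt. Read with Table 4, this is the Stage 1 look at N=15. Protocol 8.3 adds: "Enrollment will be continued after reaching the indicated number of participants at Stage 1 while the initial efficacy evaluation is ongoing".

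**Controls during the delay.** Group 1 inclusion criterion 8 (4.2.1.1) requires that surgery can be deferred for up to 12 weeks under clinical monitoring. Patients who progress leave treatment and go to definitive surgery (Synopsis, Group 1). The SRC is to "monitor the groups throughout the study overall safety and tolerability" (3.2.7), the study can be interrupted at any time (3.4), and safety is assessed continuously (8.3).

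**The concern.** The review that opens the Simon part is the only scheduled review of the run-in, yet it falls a quarter of the way through the delay that the run-in is meant to assess. Neither document says what would show the delay to be feasible or not. SAP 11.8 leaves data collection and analysis for surgical outcome to a later SAP version.

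The question matters in this population. Local-disease patients can qualify as candidates for radical excision or amputation, or as limb-salvage radiation candidates who decline radiation (4.2.1.1). The harms specific to postponing their local treatment are progression before surgery and loss of the operation that was available at entry. If these were frequent among the first six patients, the first scheduled review covering the full 12 weeks would come at N=15, after more patients had entered.

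**Working it through.** **1. The plan's own figures.** Four cycles of 21 days are 84 days, or 12 weeks, which matches the stated delay. The run-in has no operating figure or decision rule. The Group 1 Simon design (stop at ≤3/15, reject at ≤13/46; 20% against 35%) reproduces by exact two-stage binomial enumeration: alpha 0.0498, power 0.7046, early termination 0.648, expected N 25.91. These figures concern response only.

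**2. Guaranteed follow-up at the run-in review.** 21/84 = 25% of the delay. Scans are every 6 weeks with a 7-day early window (6.18), so the first falls no earlier than Day 35, after Day 21.

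**3. Likely follow-up.** Accrual is not stated, so 1, 2 and 4 patients per month are assumed, evenly spaced (month 30.44 days), with the review on Day 21 of patient 6.

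- 1 per month: 173, 143, 112, 82, 51, 21 days; 3 of 6 have reached Day 84.
- 2 per month: 97, 82, 67, 51, 36, 21 days; 1 of 6.
- 4 per month: 59, 51, 44, 36, 29, 21 days; 0 of 6.

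**4. Chance of seeing failures.** Assume a proportion p fails by week 12 at constant hazard. If failures are seen only at scheduled scans, a patient contributes p from Day 84, 1−(1−p)^0.5 from Day 42 to 83, and 0 before that. For p = 0.30 the middle value is 0.163.

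At 1 per month, three patients contribute 0.30, two contribute 0.163 and one contributes 0:

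- P(0) = 0.7³ × 0.837² = 0.240
- P(1) = 3 × 0.3 × 0.7² × 0.837² + 0.7³ × 2 × 0.163 × 0.837 = 0.402
- P(≥2) = 1 − 0.240 − 0.402 = 0.357

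With all six at Day 84, P(≥2) = 1 − 0.7⁶ − 6 × 0.3 × 0.7⁵ = 0.580.

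The other rows use the same sum. Seen at once means 1−(1−p)^(min(t,84)/84) for follow-up t. The early-window rows move the cut-offs to Days 35 and 77. They are upper limits, because an early scan still gets credit for the full interval.

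| p = 0.30, P(≥2 failures seen) | 1/month | 2/month | 4/month |
|---|---|---|---|
| Scans on Days 42 and 84 | 36% | 17% | 7% |
| Early scan window used | ≤42% | ≤30% | ≤13% |
| Early window and 14-day convening lag (assumed) | ≤48% | ≤42% | ≤26% |
| Failures seen at once, no lag | 46% | 37% | 23% |
| All six at Day 84 | 58% | 58% | 58% |

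With p = 0.50, the chance of seeing three or more is 34%, 12% or 3% (scans on Days 42 and 84, no lag) or 49%, 38% or 21% (at once), against 66% at Day 84.

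**5. Enrollment by each look.** If the N=15 evaluation waits for patient 15 to complete four cycles, 15 + floor(84/30.44), 15 + floor(84/15.22) and 15 + floor(84/7.61) give 17, 20 and 26 enrolled. When patient 6 reaches Day 84 the counts are 8, 10 and 14 if enrollment waits for the Cycle 1 review (63 further days), or 8, 11 and 17 if it does not.

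**6. A possible reference rate.** Protocol 1.1.1 gives doxorubicin in advanced disease a "median progression-free survival (PFS) of 23.3 weeks". With exponential times, 1 − 0.5^(12/23.3) = 0.30 progress by week 12. The setting differs, so this is only a guide. As an illustration, a 3-of-6 trigger fires with probability 10%, 26%, 46% or 66% at a true rate of 20%, 30%, 40% or 50%.

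**The case against.** The strongest reply is that the question is postponed rather than dropped. Run-in patients stay in the Simon part, and the evaluation at N=15 covers four cycles and histopathology and can halt the group. The wording of 3.5.1 asks for at least Cycle 1 and for all available safety data, so early enrollees will bring more than three weeks. Criterion 8 has each patient's fitness for the deferral judged before entry, and the SRC may recommend extra monitoring after any initial review. The page header in the Phase 2a SAP shows Version 0.1 with an incomplete date, so the surgical-outcome gap may be a placeholder. Because 3.2.7 ties the lead-in to 20 mL SQL70, the aim may simply be worded too broadly.

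Most of this stands, and it rules out two stronger readings. A reader might infer that nobody examines the 12-week data, or that patients are unprotected while surgery waits; the documents support neither. What remains is that the safeguards act patient by patient or on general safety. The N=15 look comes after the Simon part has started, and its numeric rule is a response count (≤3/15). The SRC is told to use the same criteria as in dose escalation, which rest on DLTs and clinical judgement, while SAP 12.6 says DLTs are not part of Phase 2a. None of these asks whether the delay is feasible for the group.

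It is also fair that a numeric stopping rule on six patients is weak. Three of six would miss a true 40% failure rate 54% of the time and pause a doxorubicin-like drug 26% of the time. Progression alone does not prove harm from delay, since progressors go to definitive surgery.

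**Conclusion.** The mismatch between aim and review is real and depends on no assumption: the stated aim needs 84 days, the scheduled review guarantees 21, and no feasibility measure is defined. As written, the run-in cannot be relied on to deliver its aim before the Simon part opens.

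The size of the consequence is less certain. The percentages rest on assumed accrual, failure rate and constant hazard. Once the early scan window and a convening lag are allowed for, the shortfall at a 30% failure rate is at least 10 points at 1 patient per month (58 − 48) and 16 points at 2 per month (58 − 42), which is small to moderate. At 4 per month it is at least 32 points (58 − 26). A reader might take the unadjusted 7% to 36% as showing that the review would usually miss a problem. That overstates the contrast, because those figures ignore the scan window and assume the SRC meets on Day 21 itself.

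Even a complete look is coarse: six of six reaching surgery as planned has an exact 95% interval of 54% to 100%. Initial feasibility is the most that six patients can show.

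**What to change.** Keep the Cycle 1 review for tolerability of 20 mL SQL70. In Protocol Table 4 and SAP 7.1, add an SRC review when the sixth run-in patient completes Cycle 4 and the presurgical re-evaluation, or leaves treatment earlier. Tie it to completion of Cycle 4, because cycles can be delayed (3.1.4.2). The review should tabulate progression before surgery and surgical status (done, deferred for response or benefit, or changed) against the plan recorded at entry, and the SRC should recommend whether to continue.

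Any numeric pause threshold or enrollment hold is for the sponsor and the SRC to set. Three of six, or a hold at 15 patients, would be illustrations only.

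If a Cycle 1 tolerability run-in is all that is wanted, restate the aim in the Synopsis, Protocol 3.5.1 and SAP 2.3 as Cycle 1 safety, PK and tolerability of 20 mL SQL70 at the RP2D.

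The added review costs one SRC meeting, about 63 days after the first if there are no treatment delays, plus wording changes. It uses visits and scans already planned and needs no extra patients. The restated aim costs wording only.

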1. INTRODUCTION

1.1. DISEASE AND TREATMENT BACKGROUND

Cancer incidence and mortality are growing worldwide ([Bray 2018](#)). In 2018, the global incidence of new cancer diagnoses was estimated at over 18 million cases, and cancer-related deaths were estimated at over 9.6 million ([Bray 2018](#)). Of these cases, the vast majority were solid tumors (more than 16 million new cases and 8 million cancer deaths). For its part, soft tissue sarcoma (STS) is a heterogeneous group of aggressive malignant tumors. In the United States (US), it is estimated that over 12,000 people were diagnosed with STS in 2019, and that, of these diagnoses greater than 5,000 individuals will die from their cancer ([Siegel 2019](#)). In Australia, over 1500 new cases of STS were diagnosed in 2014 ([Sarcoma Statistics 2019](#)). Despite improvements in early detection and treatment protocols, most patients with solid malignancies die from metastatic burden ([Chaffer & Weinberg 2011](#)).

Anthracyclines are powerful, well-established anticancer agents and among the essential tools in the chemotherapy armamentarium of medical oncologists. Doxorubicin (Dox), a cytotoxic anthracycline antibiotic isolated from cultures of *Streptomyces peucetius* var. *caesius*, has been used successfully to produce tumor regression in a variety of neoplastic conditions such as STS, acute lymphoblastic leukemia, acute myeloblastic leukemia, breast cancer, ovarian cancer, small cell lung cancer, Hodgkin lymphoma, non-Hodgkin lymphoma, gastric cancer, transitional cell bladder cancer, neuroblastoma, Kaposi's sarcoma ([Cooley 2007](#)), thyroid cancer, Wilms' tumor, and bronchogenic carcinoma (in which the small cell histologic type is the most responsive compared with other cell types) ([Arcamone 1969](#); [McGowan 2017](#)).

The antitumor activity of doxorubicin (Dox) is attributed to its interference of deoxyribonucleic acid (DNA) replication by inhibiting topoisomerase II enzyme. Despite its potent broad-spectrum antitumor activity, the extended use of conventional Dox in clinical practice is limited by life-threatening toxicities, with the most significant being largely irreversible and dose-dependent cardiotoxicity ([Jain 2000](#)). Cardiotoxicity includes short- and long-term toxic effects in the heart, ranging from alterations in myocardial structure and function, to severe cardiomyopathy and congestive heart failure (CHF). CHF was reported in > 4%, > 18%, or 36% of patients who had received cumulative conventional Dox doses of 500 to 550, 551 to 600, or > 601 mg/m², respectively ([Lefrak 1973](#)). Chronic cardiotoxicity occurred after prolonged administration of conventional Dox. Although the possibility of cardiotoxicity development is dose-dependent, it could occur even at lower doses due to individual patient variations ([Lipshultz 1995](#)). The exact causal mechanisms of Dox-induced cardiotoxicity remain elusive, making it difficult to predict or prevent its severe adverse events (AEs) in individual patients ([Ghigo 2016](#); [Whelan 2010](#); [Chiong 2011](#)). The most commonly used dose schedule of conventional Dox, as a single agent, is 60 to 75 mg/m² as a single intravenous (IV) injection every 3 weeks. The lower dosage is given to patients with inadequate marrow reserves due to old age, or prior therapy, or neoplastic marrow infiltration ([ADRIAMYCIN Australian Product Information](#); [ADRIAMYCIN US Package Insert](#)).

The cytotoxic activity of conventional Dox also affects normal cells with high turnover rates such as hematopoietic cells in the bone marrow, cells of the immune system and the gut, as well as skin and hair cells. This nonspecific cytotoxicity causes immune suppression (and associated

opportunistic infections), blood disorders, infertility, neuropathy, cognitive dysfunction, nausea, fatigue, pain, and hair loss ([Liebner 2015](#)). Bone marrow suppression is the most common acute dose-limiting toxicity (DLT) of conventional Dox; myelosuppression reaches its peak at 10 to 14 days after treatment with recovery usually occurring by the 21st day. Thrombocytopenia and anemia may also occur. Severe clinical consequences of myelosuppression include fever, infections, sepsis/septicemia, septic shock, hemorrhage, tissue hypoxia, or death ([ADRIAMYCIN Australian Product Information; ADRIAMYCIN US Package Insert](#)). These cardiac and myelosuppressive toxicities limit the dose of conventional Dox and the combination of Dox with other antineoplastic agents.

The major side effects of conventional Dox are its narrow therapeutic window and limit the acute and lifetime doses in patients ([Colombo 2015](#)). Consequently, an unmet medical need exists for novel strategies to deliver chemotherapies such as Dox with improved safety, particularly with less cardiotoxicity and broader therapeutic windows ([Frustaci 2001](#)). Consequently, an unmet medical need exists for novel strategies to deliver chemotherapies such as Dox with improved safety, particularly with less cardiotoxicity and broader therapeutic windows ([Frustaci 2001](#)). SQ3370 has the potential to address this unmet medical need.

